#### 7.7 Premature termination of the study

The study will be ended prematurely if the DSMB advises to stop the study for safety or superiority reasons (see figure 2).

## 8. SAFETY REPORTING

### 8.1 Temporary halt for reasons of subject safety

In accordance to section 10, subsection 4, of the WMO, the sponsor will suspend the study if there is sufficient ground that continuation of the study will jeopardise subject health or safety. The sponsor will notify the accredited METC without undue delay of a temporary halt including the reason for such an action. The study will be suspended pending a further positive decision by the accredited METC. The investigator will take care that all subjects are kept informed.

### 8.2 AEs, SAEs and SUSARs

All adverse events (AEs), serious adverse events (SAEs) and suspected unexpected serious adverse events (SUSARs) will be registered. The local investigator has to inform the coordinating investigator within 7 days when a SAE or SUSAR occurs.

#### 8.2.1 Adverse events (AEs)

Adverse events are defined as any undesirable experience occurring to a subject during the study, whether or not considered related to the experimental intervention.

All adverse events reported spontaneously by the subject or observed by the investigator or his staff will be recorded.

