**SUMMARY**

**Rationale:** Diabetes is a major healthcare problem with a high incidence and morbidity. Diabetic foot ulcers (DFUs) are a major complication of diabetes, often associated with peripheral arterial occlusive disease. Currently available evidence shows HyperBaric Oxygen Therapy (HBOT) can reduce major amputation rate, but clinicians remain sceptical about the (cost-) effectiveness and feasibility of HBOT for ischemic DFUs in clinical practice. Therefore, international vascular surgeons and HBOT-physicians feel a strong need for a sufficiently powered clinical trial to determine whether and how many HBOT-sessions may be a (cost-) effective adjunctive treatment to ischemic DFUs.

**Objective:** The primary objective is to assess the (cost-) effectiveness of HBOT in addition to standard wound care and vascular surgical treatment for patients with a DFU and leg ischemia.

**Study design:** An international, multi-arm multi-stage (MAMS) design is chosen to conduct an efficient randomised clinical trial. At a planned interim analysis the best performing study arm(s) will be chosen to continue.

**Study population:** We need up to 544 patients with a Meggitt-Wagner stage 3 or 4 DFU and proven peripheral ischaemia.

**Intervention:** Patients will be randomised to receive standard care (wound treatment and surgical interventions following international guidelines) with either 0, 20, 30 or 40 sessions of HBOT. These sessions will comprise 90-120 minutes of HBOT at a pressure of 2.2-2.5 ATA according to international standards.

**Main study parameters/endpoints:** Primary endpoints are amputation rates and amputation-free survival after 12 months. Secondary objectives are wound healing, health-related quality of life and cost-effectiveness of the interventions.

**Nature and extent of the burden and risks associated with participation, benefit and group relatedness:** All patients will receive standard wound care and (if possible) endovascular or surgical revascularization, irrespective of their allocation. HBOT is a generally accepted and reimbursed indication for the treatment of DFUs. The risks of HBOT are regarded as low. Patients in the HBOT groups will undergo 20, 30 or 40 HBOT sessions. Patients will be asked to fill in questionnaires at four time points, and to score their pain weekly during the first 8 weeks. Three visits to their outpatient surgical clinic will be scheduled, which do not deviate from usual care.

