### 3. STUDY DESIGN

Multinational randomized clinical trial with an adaptive (multi-arm, multi-stage; MAMS) design, with a follow-up of 12 months, following the (extended) CONSORT-statement. We will have four study arms and two stages (one interim and one final analysis; see figure 1 below). Patients will be randomized to receive standard treatment with 0, 20, 30 or 40 HBOT treatments.

The more efficient MAMS design (Sydes 2018, Sydes 2012, Wason 2012) for clinical trials includes a planned interim analysis, based on which only the best performing study arms will be chosen to continue. This will reduce the total number of patients required and the number of patients receiving an ineffective treatment, because after the interim analysis no patients will be included in less effective treatment arms.

[figure not shown]

Figure 1 Flow of patient inclusion and analysis

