## 5. TREATMENT OF SUBJECTS

### 5.1 Investigational product/treatment

Patients allocated to the intervention group will receive 20, 30 or 40 sessions of HBOT adjunctive to standard care, as determined by the randomisation. A HBOT session will take 90 to 120 minutes at 2.2-2.5 ATA. Besides the 90-120 minutes of treatment, approximately 20 minutes are required for compression and decompression. During the treatment session the patients will breathe 100% FiO2 except for 3 blocks of 5 minutes during which atmospheric air will be administered to prevent oxygen intoxication. This HBOT-regimen has been approved by the hyperbaric medicine specialists from all contributing HBOT-centers as the optimum and safest HBOT procedure for these patients. Patients will either lay in bed or sit in a chair during the session. At least for the first time, cabin personnel will accompany patients in the cabin and instruct them about the use of the oxygen masks or hoods. The cabin will be pressurized gradually in about 10 minutes. Subsequently, the supervising staff member will supply patients with masks through which the oxygen will be administered. The staff member will then leave the cabin, but will remain in constant contact with the patients through cameras and microphones. In case of adverse events requiring termination of the session, patients will be able to leave the cabin after a short decompression period. After the treatment, the cabin will be decompressed in about 10 minutes.

HBOT will be administered in a hyperbaric chamber. HBOT is preferably given 5 times per week, but at least 3 times per week, until the total number of sessions has been reached. To minimize interruption of HBOT and masking of the effect by additional vascular interventions, any (additional) (endo)vascular procedure will preferably be performed after randomisation but before the start of HBOT treatment. In case a vascular intervention is required (due to progression of the disease) while the patient is undergoing the HBOT sessions, these are interrupted for the period of the vascular intervention and continued directly afterwards until completion of the sessions.

[figure not shown]

Figure 3 Example of HBOT tabel

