### 7.3 Study procedures

Patients from each (remaining) study arm will be monitored up to 36 months after randomisation. At the start of the trial, patients' baseline characteristics will be obtained. Pain scores will be collected through first phase of the trial. Questionnaires will be completed at baseline and will be sent to the patients' home after 3 months and 1 year.

Amputation rate, ulcer recurrence, additional interventions, mortality, adverse events and costs will be monitored after 1 year and 3 years.

Assessment	Before randomisation	Week 1-8, once a week	After 3 months	After 1 year	After 3 years
Patient characteristics	*				
Meggitt-Wagner classification	*		*	*	
Wound measurements	*				
Ankle blood pressure	*		*	*	
Toe systolic pressure	*		*	*	
TcPO2	*		*	*	
VAS		*	*	*	
Freedom of amputation			*	*	*
Complete ulcer healing			*	*	*
Recurrent ulcer			*	*	*
Nr of additional vascular events		*	*	*	*
Adverse events		*	*	*	
Patient's out of pocket expenses			*		
Questionnaires	*		*	*	*

*Table 1 Assessments and follow-up*

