## 9. STATISTICAL ANALYSIS

All analyses will be conducted according to the intention-to-treat principle. Baseline characteristics are summarized with descriptive statistics. Differences between dichotomous variables (like the amputation rate) will be expressed as a risk differences and Numbers Needed to Treat or Harm. Statistical precision will be expressed as 95% confidence intervals. Differences between continuous variable will be expressed as difference in means. If outcome parameters are unevenly distributed, they will be expressed as medians and inter-quartile ranges.

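### Adverse events are recorded on spontaneous report or staff observation, with no common questioning stated, while only the HBOT arms have 20, 30 or 40 staff-observed sessions, so any comparison of non-serious events risks unequal ascertainment

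*Protocol*

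**What the plan says.** - **Recording rule (8.2 and 8.2.1).** Section 8.2 is general: "All adverse events (AEs), serious adverse events (SAEs) and suspected unexpected serious adverse events (SUSARs) will be registered". Section 8.2.1 is the only place that says how an event comes to be recorded: "All adverse events reported spontaneously by the subject or observed by the investigator or his staff will be recorded".
- **Arms (section 3).** "Patients will be randomized to receive standard treatment with 0, 20, 30 or 40 HBOT treatments". No sham session is described, and section 7.2 covers concealed allocation but describes no blinding.
- **Contact in the HBOT arms (5.1).** "HBOT is preferably given 5 times per week, but at least 3 times per week, until the total number of sessions has been reached". During a session, "The staff member will then leave the cabin, but will remain in constant contact with the patients through cameras and microphones".
- **Contact in all arms (Summary).** "Three visits to their outpatient surgical clinic will be scheduled, which do not deviate from usual care". Patients also score their pain weekly for the first 8 weeks.
- **Schedule (7.3).** Table 1 marks adverse events under "Week 1-8, once a week", at 3 months and at 1 year, without distinguishing arms. The running text of the same section names 1 year and 3 years for adverse events.
- **Use of the data.** Section 9 says that differences in dichotomous variables "will be expressed as a risk differences and Numbers Needed to Treat or Harm". The one harm parameter listed, in 7.1.3, is complications caused by HBOT itself. Section 8.3 asks for an evaluation of efficacy against harm, and under 8.5 the DSMB advises on safety.

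**The concern.** When an event enters the record because someone mentions it or a staff member sees it, the chance of recording depends on how often patient and staff meet. Here the randomisation sets much of that contact. A minor event with the same true frequency in all four arms (a fall, a hypoglycaemic episode, a mild infection) has more chances to be noted in a patient attending a chamber three to five times a week than in a control patient. It also has more chances over 40 sessions than over 20.

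If non-serious events are then compared between arms as risk differences or numbers needed to harm, part of any excess under HBOT could come from contact alone, and a gradient over session number could resemble dose-related toxicity. This has to be settled in data collection: an event never elicited in a control patient cannot be recovered at analysis.

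**Working it through.** The protocol gives no adverse-event rate or capture rate, so there is no stated figure to reproduce. Two checks are possible.

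**1. Occasions on which an event can be recorded, to 1 year**

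From Table 1: 8 weekly checks + 1 at 3 months + 1 at 1 year = 10 in every arm. Sessions come from section 3, and course length is sessions divided by 5 or by 3 per week (5.1).

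| Arm | Course at 5/week | Course at 3/week | Scheduled + sessions | Ratio to control |
|---|---|---|---|---|
| 0 | none | none | 10 + 0 = 10 | 1 |
| 20 | 4 weeks | 6.7 weeks | 10 + 20 = 30 | 3 |
| 30 | 6 weeks | 10 weeks | 10 + 30 = 40 | 4 |
| 40 | 8 weeks | 13.3 weeks | 10 + 40 = 50 | 5 |

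Even with every Table 1 check credited to control, opportunity is 1 : 3 : 4 : 5. At 5 sessions per week, weeks 1-8 span the whole 40-session course. At 3 per week, the 30- and 40-session courses run 2 and 5.3 weeks beyond week 8, when Table 1 has no check until 3 months.

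**2. How much this could matter**

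Assumptions, none from the documents:
- true risk R = 30% in every arm, with event time uniform over 13 weeks;
- an event is volunteered anyway with probability v = 0.3 to 0.7;
- each later session reveals an unrecorded event with probability q = 0.02 to 0.05;
- sessions run at 5 per week, so n sessions last n/5 weeks;
- each later scheduled check (weeks 1-8 and week 13) reveals it with probability s.

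With s = 0, averaging over event time gives

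excess over control = R × (1 − v) × (n/5)/13 × [1 − (1 − (1 − q)^n)/(nq)].

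- Largest case, n = 40, v = 0.3, q = 0.05: 0.95^40 = 0.1285. The bracket is 1 − 0.8715/2 = 0.564. Excess = 0.30 × 0.7 × 8/13 × 0.564 = 0.073, or 7.3 points.
- Smallest case, n = 20, v = 0.7, q = 0.02: 0.98^20 = 0.668. The bracket is 1 − 0.332/0.4 = 0.169. Excess = 0.30 × 0.3 × 4/13 × 0.169 = 0.005, or 0.5 points.

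For s > 0, the chance that an event stays unrecorded is also multiplied by (1 − s) for each remaining check, and the average was taken numerically.

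| Spurious excess, points | 20 sessions | 30 sessions | 40 sessions |
|---|---|---|---|
| s = 0 (checks elicit nothing) | 0.5-2.3 | 1.0-4.6 | 1.7-7.3 |
| s = 0.3 | at most 0.1 | at most 0.4 | at most 0.9 |
| s = 0.8 | about 0 | about 0 | about 0 |

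The excess is proportional to R. Within this model the result depends mostly on s, that is, on whether patients are actually asked at the Table 1 points, and the protocol does not state this.

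**The case against.** The strongest reply is that 8.2.1 is inclusive. It does not say that volunteered or observed events are the only ones recorded, 8.2 registers all events, and Table 1 gives every arm ten scheduled occasions. The weekly column also carries the pain score, so some weekly contact exists in control. This stands in part: control is not without scheduled capture, and if the checks include questioning, the problem nearly disappears. But with three clinic visits in the Summary, the eight weekly entries cannot all be visits. Nothing says that patients are asked about events there, and the text of 7.3 gives other times.

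Control patients are also seen by staff for wound and vascular care (5.2, 10.4), and the protocol does not say whether chamber operators count as the investigator's staff. Both points stand and would shrink the difference.

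A reader might infer that HBOT harm will certainly be overstated, or that the choice of session number will be biased. The documents support neither:
- The size, and whether there is any material bias at all, rests on assumed capture rates.
- Section 4.4 drops, continues or selects arms on amputation rate alone, and picks the fewest sessions if several arms are superior.
- No adverse-event comparison with control is named. The sentence in section 9 is general, with amputation as its example.
- Finding the 7.1.3 complications at sessions is correct ascertainment.

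It could also be said that elicitation is operational detail. That would carry more weight had the protocol left the method open. Instead, 8.2.1 states a passive rule.

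**Conclusion.** The point holds as a risk, not as a demonstrated bias. The stated recording rule depends on contact, and contact differs by arm at 1 : 3 : 4 : 5 occasions in a trial with no blinding described. The likely direction is more recorded non-serious events under HBOT, possibly rising with session number. The range of about 0 to 7 percentage points is illustrative and rests entirely on the assumptions listed above. Deaths and hospital admissions depend less on session contact, so SAEs are less exposed. The disagreement between Table 1 and the text of 7.3 on when adverse events are monitored needs no assumption: it is plain on the page. This is a cheap improvement and does not threaten the primary analysis.

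**What to change.** 1. Reconcile 8.2.1, Table 1 and the text of 7.3 so that they give one schedule and one method for adverse events.
2. State in 8.2.1 that non-serious adverse events are solicited with the same short question set in all four arms at the Table 1 time points, in weeks 1-8 alongside the weekly pain score. Every event from any source is still recorded and reported as now.
3. Add a source field to the eCRF: common time point, HBOT session, or spontaneous report.
4. State in section 9 that any between-arm adverse-event comparison is accompanied by a sensitivity analysis limited to events captured at the common time points plus SAEs. Making that restriction the main comparison would be debatable, because it discards real events.

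Cost: a few items added to a weekly score that all arms already give, one data field and a few sentences of text, with no extra visits. The downside is slightly more patient burden and more non-serious events to record.

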#### 8.2.2 Serious adverse events (SAEs)

A serious adverse event is any untoward medical occurrence or effect that

- results in death;
- is life threatening (at the time of the event);
- requires hospitalisation or prolongation of existing inpatients' hospitalisation;
- results in persistent or significant disability or incapacity;
- is a congenital anomaly or birth defect; or
- any other important medical event that did not result in any of the outcomes listed above due to medical or surgical intervention but could have been based upon appropriate judgement by the investigator.

An elective hospital admission will not be considered as a serious adverse event.

The investigator will report all SAEs to the sponsor without undue delay after obtaining knowledge of the events.

The sponsor will report the SAEs through the web portal *ToetsingOnline* to the accredited METC that approved the protocol, within 7 days of first knowledge for

SAEs that result in death or are life threatening followed by a period of maximum of 8 days to complete the initial preliminary report. All other SAEs will be reported within a period of maximum 15 days after the sponsor has first knowledge of the serious adverse events.

### **8.2.3 Suspected unexpected serious adverse reactions (SUSARs)**

Adverse reactions are all untoward and unintended responses to an investigational product related to any dose administered.

Unexpected adverse reactions are SUSARs if the following three conditions are met:

1. the event must be serious (see chapter 9.2.2);
2. there must be a certain degree of probability that the event is a harmful and an undesirable reaction to the medicinal product under investigation, regardless of the administered dose;
3. the adverse reaction must be unexpected, that is to say, the nature and severity of the adverse reaction are not in agreement with the product information as recorded in:
  - Summary of Product Characteristics (SPC) for an authorised medicinal product;
  - Investigator's Brochure for an unauthorised medicinal product.

The sponsor will report expedited the following SUSARs through the web portal *ToetsingOnline* to the METC

- SUSARs that have arisen in the clinical trial that was assessed by the METC;
- SUSARs that have arisen in other clinical trials of the same sponsor and with the same medicinal product, and that could have consequences for the safety of the subjects involved in the clinical trial that was assessed by the METC.

The remaining SUSARs are recorded in an overview list (line-listing) that will be submitted once every half year to the METC. This line-listing provides an overview of all SUSARs from the study medicine, accompanied by a brief report highlighting the main points of concern.

The expedited reporting of SUSARs through the web portal Eudravigilance or *ToetsingOnline* is sufficient as notification to the competent authority.

The sponsor will report expedited all SUSARs to the competent authorities in other Member States, according to the requirements of the Member States.

The expedited reporting will occur not later than 15 days after the sponsor has first knowledge of the adverse reactions. For fatal or life threatening cases the term will be maximal 7 days for a preliminary report with another 8 days for completion of the report.

### **8.3 Annual safety report**

In addition to the expedited reporting of SUSARs, the sponsor will submit, once a year throughout the clinical trial, a safety report to the accredited METC, competent authority, and competent authorities of the concerned Member States.

This safety report consists of:

- a list of all suspected (unexpected or expected) serious adverse reactions, along with an aggregated summary table of all reported serious adverse reactions, ordered by organ system, per study;
- a report concerning the safety of the subjects, consisting of a complete safety analysis and an evaluation of the balance between the efficacy and the harmfulness of the medicine under investigation.

### **8.4 Follow-up of adverse events**

All AEs will be followed until they have abated, or until a stable situation has been reached. Depending on the event, follow up may require additional tests or medical procedures as indicated, and/or referral to the general physician or a medical specialist. SAEs need to be reported till end of study within the Netherlands, as defined in the protocol

### **8.5 Data Safety Monitoring Board (DSMB)**

An independent DSMB, consisting of a statistician, an diabetologist and an independent vascular surgeon, is established prior to the start of the trial. The purpose of the DSMB is to advise the DIONYSIUS-trial investigators whether it is safe to continue the study. Interim-analyses will be performed after inclusion of 25%, 50% and 75% of the patients. The advice(s) of the DSMB will only be sent to the sponsor of the study. Should the sponsor decide not to fully implement the advice of the DSMB, the sponsor will send the advice to the reviewing METC, including a note to substantiate why (part of) the advice of the DSMB will not be followed. If a risk is detected that endangers patients, the study will be terminated prematurely.

## 9. STATISTICAL ANALYSIS

All analyses will be conducted according to the intention-to-treat principle. Baseline characteristics are summarized with descriptive statistics. Differences between dichotomous variables (like the amputation rate) will be expressed as a risk differences and Numbers Needed to Treat or Harm. Statistical precision will be expressed as 95% confidence intervals. Differences between continuous variable will be expressed as difference in means. If outcome parameters are unevenly distributed, they will be expressed as medians and inter-quartile ranges.

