The largest and most recent DAMOCLES trial on HBOT for ischemic DFUs (Santema 2018a) showed some promising results for HBOT as an adjunctive treatment for patients with ischemic DFUs. However, the treatment effect was not convincing, due to the limited number of patients available for inclusion in a single country, as well as the inclusion of relatively superficial, uninfected (Meggitt-Wagner class 2) DFUs (Santema 2018b). They found 10% fewer major amputations after 12 months in patients treated with HBOT in their intention-to-treat analysis, but this was not statistically significant. In the per-protocol analysis a significant reduction of major amputations (17%) observed. Amputation-free survival (AFS) after HBOT was 13% higher in the intention-to-treat analysis, which was not statistically significant. In the per-protocol analysis the AFS was significantly (26%) higher as opposed to standard treatment. No significant effect was found on complete ulcer healing in neither the intention-to-treat nor the per-protocol analysis.

The recent meta-analysis (Brouwer 2020) of currently available evidence shows that HBOT may lead to a 15% reduction of major amputation rate, but shows no effect on minor amputation, CUH, or mortality. To date, substantial scepticism still exists among clinicians due to the limited and conflicting evidence for its (cost-)effectiveness to promote wound healing and prevention amputations or amputation-free survival. Hence, a strong need is felt internationally among vascular surgeons and HT-physicians for a sufficiently powered clinical trial that is able to determine whether HBOT is a (cost-)effective treatment for ischemic DFUs.

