## 2. OBJECTIVES

The aim of the study is to confirm or refute the hypothesis that HBOT is (cost-) effective as an adjunctive treatment to standard wound care for patients with an ischemic DFU to prevent major amputations and to establish the optimal number of sessions to obtain this purported effect.

Primary Objective:

Amputation rate and amputation-free survival

Secondary Objective(s):

- Cost-effectiveness and budget impact
- Complete wound healing
- Health-related quality of life
- Pain scores
- Need for additional (vascular) interventions
- TcpO2 before, during and after HBOT

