## **4. STUDY POPULATION**

### **4.1 Population (base)**

Consecutive patients with type I or II diabetes, a DFU and leg ischemia, presenting at the vascular surgery departments of the participating hospital. Also, HBOT centers and general practitioners may refer patients to the vascular surgery departments for inclusion in the study. Both patients suitable and unsuitable for vascular repair are eligible for inclusion.

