**5.2 Use of co-intervention (if applicable)**

HBOT will be given in addition to standard care according to local best practice in expertise centers and will not intervene with the usual care. Although (vascular) interventions are preferably performed before the start of HBOT, participation in the study will not influence any additional interventions that might be needed during follow-up ((endo)vascular interventions, amputations, wound debridement, medication, etc).

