#### 7.1.3 Other study parameters (if applicable)

- Complications directly related to HBOT treatment (e.g. middle ear and sinus barotrauma, epileptic seizure, myopia)

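### The intention-to-treat rule covers all analyses, so complications caused by HBOT are divided by everyone allocated, including patients who never start it

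*Protocol*

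**What the plan says.** Section 9 of the Protocol opens with one rule for the whole analysis: "All analyses will be conducted according to the intention-to-treat principle". It adds that differences in dichotomous outcomes are "expressed as a risk differences and Numbers Needed to Treat or Harm". No section defines a safety population or any analysis by treatment received.

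Section 7.1.3 names as a study parameter "Complications directly related to HBOT treatment (e.g. middle ear and sinus barotrauma, epileptic seizure, myopia" (the list closes there). These events are defined by their cause, which is the HBOT session itself.

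Section 3 sets the arms: "Patients will be randomized to receive standard treatment with 0, 20, 30 or 40 HBOT treatments". Sections 7.1 and 7.1.2 provide for collecting treatment volumes and HBOT costs for the economic evaluation. The assessment table in section 7.3 lists adverse events but has no row for sessions received.

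**The concern.** Analysis by allocation suits amputation, amputation-free survival and the economic outcomes. There it preserves the randomised comparison, and any dilution from incomplete treatment is part of the question asked.

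For an event that only exposure can cause, it errs towards making the treatment look safer than it is. A patient allocated to 20, 30 or 40 sessions who never starts adds one to the denominator and cannot add to the numerator. A patient in the 0-session arm who nevertheless received HBOT and had barotrauma would be counted as a control complication, which narrows the difference between arms further. The reported risk of harm, and the number needed to harm built on it, would then understate what a treated patient faces.

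The point does not depend on what a statistical analysis plan may add. The Protocol has already fixed a rule for every analysis, so a later plan with a treated-patients safety set would contradict it.

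**Working it through.** **The plan's own figures.** The Protocol gives no expected complication rate, never-start share or crossover share, so there is no figure to reproduce. What follows uses assumed ranges.

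**Inputs**
- Analysis set: everyone allocated (section 9).
- Outcome: complications directly related to HBOT (section 7.1.3). By definition these are zero in patients with no session.
- r = complication rate among patients with at least one session (assumed 10% and 20%).
- n = share of an HBOT arm that never starts (assumed 5%, 10%, 20%).
- c = share of the 0-session arm that receives HBOT during follow-up (assumed 0% and 10%), with the same rate r once exposed.

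**Step 1: rate in an HBOT arm by allocation.** Reported rate = r × (1 − n) + 0 × n = r × (1 − n). The relative understatement is n, whatever r is.

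| Never start (n) | r = 10% reads | r = 20% reads |
|---|---|---|
| 5% | 10 × 0.95 = 9.5% | 20 × 0.95 = 19% |
| 10% | 10 × 0.90 = 9.0% | 20 × 0.90 = 18% |
| 20% | 10 × 0.80 = 8.0% | 20 × 0.80 = 16% |

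In counts: of 100 allocated, 90 start and 9 have a complication. By allocation this is 9/100 = 9.0%; among treated patients it is 9/90 = 10%.

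**Step 2: number needed to harm, no HBOT in controls.** It equals 1 / (risk difference from control). With r = 10% it is 1/0.10 = 10 among treated patients. By allocation it is 1/0.095 = 10.5, 1/0.090 = 11.1 or 1/0.080 = 12.5 for n = 5%, 10% or 20%.

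**Step 3: adding HBOT in controls.** Risk difference = r × (1 − n) − r × c = r × (1 − n − c). With r = 10% and c = 10%:
- n = 10%: 10 × 0.80 = 8.0 points
- n = 20%: 10 × 0.70 = 7.0 points

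**Step 4: who causes the dilution.** A patient who has a few sessions and then stops has been exposed, and a complication is counted in the allocated arm. Early stopping therefore does not dilute a per-patient rate; only patients who never start do. Early stopping matters only when a rate is expressed per session, which requires the number of sessions delivered.

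**The case against.** The other side has a good deal to say.

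- **Complications are a minor parameter.** They are listed under other study parameters, section 9.2 names no test for them, and section 8.2 has all adverse events registered whatever the analysis set. This stands and limits the consequence. The rate and the number needed to harm still fall under the section 9 rule as written.
- **HBOT use in controls is not documented.** The only explicit mention of HBOT outside allocation is in section 7.6. It concerns patients who withdraw and are not followed, so no analysis set would capture their events. For controls who stay in the trial it is an inference: HBOT is reimbursed (section 1), section 4.1 says "HBOT centers and general practitioners may refer patients to the vascular surgery departments for inclusion in the study", and section 5.2, which does not name HBOT, says "participation in the study will not influence any additional interventions that might be needed during follow-up". None of this is evidence that crossover will occur. The control part of the point is therefore conditional.
- **Sessions received may already be collected.** The volumes and costs in sections 7.1 and 7.1.2 largely require session counts. This stands, and it makes the fix cheap.

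A reader might also infer three stronger points that the documents do not support.

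- **That the aim "to establish the optimal number of sessions to obtain this purported effect" is answered wrongly because arms are compared on sessions assigned.** Comparison by allocation is the valid randomised answer to which prescribed number is best. A supplementary adherence analysis is commonly left to the statistical analysis plan, and a complier-average effect would need further assumptions with three session numbers and partial receipt.
- **That the earlier trial shows how many patients go untreated.** Section 1 reports 10% fewer major amputations by intention-to-treat, and then "In the per-protocol analysis a significant reduction of major amputations (17%) observed". The ratio 10/17 compares two efficacy differences. It is not the share of patients treated, and the per-protocol figure carries selection. No dilution of complications or efficacy can be derived from it.
- **That complications should be grouped by sessions received.** Section 12.1 (item j) stops treatment after a seizure or signs of pulmonary toxicity, so events would collect in the low-session groups because the event ended the course.

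**Conclusion.** The point holds for the safety denominator. Section 9 places complications caused by HBOT under intention-to-treat without exception, and this understates the rate in each HBOT arm by exactly the share who never start. Under the assumed range of 5% to 20% never starting, a true 10% reads 9.5% to 8.0%, and the number needed to harm moves from 10 to between 10.5 and 12.5. If some controls received HBOT, the difference from control would shrink further.

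This assumes that such complications cannot occur without a session, and that controls who cross over have the same rate as other treated patients. The true size is unknown because the Protocol gives no never-start or crossover rate; if every allocated patient starts and no control is exposed, the bias is zero. It is a modest but definite flaw of wording, in the direction that makes treatment look safer. Intention-to-treat for efficacy is not in question.

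**What to change.** 1. In section 9, limit the intention-to-treat sentence to efficacy and economic analyses, and keep allocation to the assigned session number as the basis for these.
2. State that HBOT-related complications (section 7.1.3) are reported among patients who received at least one session, by allocated arm, and also as events per session delivered. Show any control patient who received HBOT separately.
3. Record the number of HBOT sessions received in all four arms, so that both denominators exist. Most of this is already needed for the volumes and costs in sections 7.1 and 7.1.2.

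The cost is one change of wording, slightly more data recording (mainly in the 0-session arm), and complication rates that look somewhat less favourable. Sample size, randomisation, the interim rules and the primary analysis stay as they are.
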